10.1.6. AE Evaluation Period

In this study, the AE evaluation period will be from the “the start day of the administration of the investigational drug” to “30 days after the day of the last dose of the investigational drug, or if subsequent treatment is initiated before that, before the start of the subsequent treatment, whichever comes earlier.” AEs occurring this period will be collected.

Even if it is 31 days after the last dose of the investigational drug, AEs assessed as related to the protocol treatment should be collected.

After PD is conformed, it is unnecessary to collect newly occurred AEs associated with the progression of the primary disease.

10.2. Reporting of Serious Adverse Events (SAEs)

10.2.1. Definition of SAE

Of the AEs specified in the Section “10.1 Evaluation of AEs” AEs falling into any of the following items are defined as “SAEs.”

- (1) An event that results in death or is life-threatening;
- (2) An event that results in persistent or significant disability/incapacity;
- (3) An event that is a congenital anomaly/congenital defect; or
- (4) An event that requires inpatient hospitalization or prolongation of existing hospitalization

However, excluding the following events:

- Hospitalization or death due to the primary disease after PD is confirmed;
- Hospitalization or prolongation of existing hospitalization for reducing a burden to a patient who visits the hospital from a remote place;
- Hospitalization or prolongation of existing hospitalization planned beforehand;
- Hospitalization or prolongation of existing hospitalization not related to AEs; or
- Hospitalization or prolongation of existing hospitalization for no more than 24 hours only for following up of the course.

- (5) Medically important events are defined as those which possibly jeopardize the

patient or require a medical or surgical intervention to prevent the outcomes listed above.

Note: In addition to the above criteria, adverse events meeting either of the below criteria, although not serious per ICH definition, must be reported within 24 hours to the Sponsor and within 2 working days of but not longer than three 3 calendar days of receipt of the information to Merck Global Safety Providerz to meet certain local requirements. Therefore, these events are considered serious by Provider for collection purposes.

- Is a new cancer (that is not a condition of the study);
- Is associated with an overdose

For the time period beginning when the consent form is signed until treatment, any serious adverse event, or follow up to a serious adverse event, including death due to any cause that occurs to any participant must be reported within 24 hours to the Sponsor and within 2 working days of but not longer than three 3 calendar days of receipt of the information to Merck Global Safety if it causes the participant to be excluded from the trial, or is the result of a protocol-specified intervention, including but not limited to washout or discontinuation of usual therapy, diet, placebo treatment or a procedure.

For the time period beginning at treatment through 90 days following cessation of treatment, or 30 days following cessation of treatment if the participant initiates new anticancer therapy, whichever is earlier, any serious adverse event, or follow up to a serious adverse event, including death due to any cause whether or not related to the Provider product, must be reported within 24 hours to the Sponsor and within 2 working days of but not longer than three 3 calendar days of receipt of the information to Merck Global Safety.

Additionally, any serious adverse event, considered by an investigator who is a qualified physician to be related to Provider product that is brought to the attention of the investigator at any time following consent through the end of the specified safety follow-up period specified in the paragraph above, or at any time outside of the time period specified in the previous paragraph also must be reported immediately to Merck Global Safety.

All participants with serious adverse events must be followed up for outcome.

SAE reports and any other relevant safety information are to be forwarded to the Merck Global Safety [contact]

10.2.2. . Reporting Obligation of the Investigator and Reporting Procedures

1) Report to the head of the study site and the coordinating committee

① Initial report

When an SAE (see the Section “10.2”) occurred, the investigator should immediately take an appropriate action. The subinvestigators should promptly report it to the principal investigator.

The investigator should report an SAE occurred in writing (e-mail* or fax) or orally (telephone) to the head of the study site and the coordinating committee within 24 hours after learning its onset. When the initial report is made without using the “SAE Report,” a report should be promptly made using the said form (e-mail or fax).

In addition, the details of the SAE should be reported in writing to the head of the study site and the coordinating committee within 2 business days after learning its onset.

* Reporting by e-mail is recommended.

② Additional report

The principal investigator should follow up the SAE (see the Section “10.2”). Additional information should be recorded in the “SAE Report” (additional report) and promptly sent to the head of the study site and the coordinating committee within 2 days after learning its onset.

Contact information of the coordinating committee: Clinical Study Coordinating Secretariat

E-mail: [contact]

[contact] ([name]) [contact]

The investigator should provide further information upon request of the coordinating committee, the head of the study site, the institutional review board (IRB) and the investigational drug suppliers.

10.2.3. Reporting Obligation of the Coordinating Committee and Reporting Procedures

The coordinating committee should determine the seriousness, causal relationship, expectedness and the necessity for reporting to the regulatory authority (Pharmaceuticals and Medical Devices Agency (PMDA)) (pursuant to “Article 80-2, Paragraph 6 of the Pharmaceutical Affairs Law (PAL)” and “Article 273 of the Enforcement Regulations of the PAL”) for SAEs notified by initial and additional reports.

The details of reporting procedures should be as specified in the “Procedures for Handling

of Safety Information."

1) Report to each principal investigator

The coordinating committee should promptly report the notified SAE with the details of the abovementioned determinations to each principal investigator. Each principal investigator should, as necessary, report them as soon as possible to the head of the study site in accordance with rules at each study site.

2) Report to the PMDA

When reporting to the PMDA is found necessary, the coordinating committee should handle the matter in accordance with Article 273 of the Enforcement Regulations of the PAL and relevant notifications.

3) Report to the efficacy and safety evaluation committee

When a review of an SAE by the efficacy and safety evaluation committee is judged to be necessary, the coordinating committee should report it in writing and seek its opinions on the appropriateness of the comments of the principal investigator and coordinating committee on the AE and handling (assessments of the seriousness, causal relationship and expectedness of the AE) of the AE.

4) Report to the investigational drug suppliers

The coordinating committee should promptly notify SAEs reported by the investigator to the investigational drug suppliers. In addition, the coordinating committee should, as necessary, provide information other than the "SAE Report" to the investigational drug suppliers upon their request.

10.2.4. Events of Clinical Interest

10.2.4.1. Definition of ECI

Events of clinical interest for this trial include:

1. an elevated AST or ALT lab value that is greater than or equal to 3X the upper limit of normal and an elevated total bilirubin lab value that is greater than or equal to 2X the upper limit of normal and, at the same time, an alkaline phosphatase lab value that is less than 2X the upper limit of normal, as determined by way of protocol-specified laboratory testing or unscheduled laboratory testing.*

*Note: These criteria are based upon available regulatory guidance documents. The purpose of the criteria is to specify a threshold of abnormal hepatic tests that may require an additional evaluation for an underlying etiology.

2. an overdose of Provider product, as defined in Section 7.2.1 - Definition of an Overdose for This Protocol and Reporting of Overdose to the Sponsor, that is not associated with clinical symptoms or abnormal laboratory results.

10.2.4.2. Reporting of ECI

Selection non serious and serious adverse events are also known as Events of Clinical Interest (ECI) and must be reported within 2 working days of but not longer than 3 calendar days of receipt of information. But, if it should be the serious adverse events, you don't have any duty to report to the head of the institution.

For the time period beginning at treatment through 90 days following cessation of

treatment, or 30 days following cessation of treatment if the participant initiates new anticancer therapy, whichever is earlier, any ECI, or follow up to an ECI, whether or not related to Provider product, must be reported within 2 working days of but not longer than three 3 calendar days of receipt of the information.

10.2.5. Duties of the Efficacy and Safety Evaluation Committee

The efficacy and safety evaluation committee should examine the details of AE reports and advise, in writing, handling such as whether or not to continue the study and the necessity of protocol revisions to the coordinating committee. For their procedures, the separately stipulated “Procedures for the Efficacy and Safety Evaluation Committee” should be followed.

10.3. Collection of Safety Information

When safety information on the investigational drugs is received from the investigational drug suppliers, the coordinating committee should handle it in accordance with Article 273 of the Enforcement Regulations of the PAL and relevant notifications. The coordinating committee should report the safety information to each principal investigator. Each principal investigator should report it to the head of the study site as soon as possible in accordance with rules at each study site.

For the details of reporting procedures, the “Procedures for Handling of Safety Information” should be followed.

In addition, the necessity of revising the protocol and written information to patients as well as an explanation to the patients should be determined and implemented if needed.

10.4. Reporting of Pregnancy and Lactation

Although pregnancy and lactation are not considered adverse events, it is the responsibility of investigators or their designees to report any pregnancy (subject or partner of a male subject) or lactation in a subject (spontaneously reported to them) that occurs during the trial.

Pregnancies and lactations that occur from the time of treatment enrollment through 120 days following cessation of Pembrolizumab, or 30 days following cessation of treatment if the subject initiates new anticancer therapy, whichever is earlier, must be reported by the investigator. All reported pregnancies must be followed to the completion/termination of the pregnancy. Pregnancy outcomes of spontaneous abortion, missed abortion, benign hydatidiform mole, blighted ovum, fetal death, intrauterine death, miscarriage and stillbirth must be reported as serious

events (Important Medical Events). If the pregnancy continues to term, the outcome (health of infant) must also be reported.

Such events must be reported within 24 hours to the Principal Investigator. Such events must be reported to Eisai corporation and within 2 working days of but not longer than three 3 calendar days of receipt of the information to Merck Global Safety. (Attn: Worldwide Product Safety; [contact])

11. ASSESSMENT OF RESPONSE AND DEFINITIONS OF THE ENDPOINTS

11.1. Assessment of Response

Assessments of tumor response should be made in accordance with the RECIST guideline Ver 1.1 (Appendices 2).

Chest and abdomen and pelvic contrast CT or MRI (Simple CT or MRI is acceptable if the patients are allergic to contrast media.) should be performed in accordance with Table 8.b to make the assessments based on image measurements.

11.2. Definitions of the Endpoints

11.2.1. Objective response rate:ORR

The ORR will be defined as the proportion of patients who achieved CR or PR for best overall response (confirmation required) according to irRECIST and RECIST v1.1.

11.2.2. Progression free survival:PFS

The period will be from the day of enrollment, as the starting date of the computation, to the day when progression is determined or the day of death of any cause, whichever comes earlier.

- “Progression” will be PD based on diagnostic imaging according to overall response by RECIST v1.1. The day of the imaging test will be defined as the day of progression. When the treatment are discontinued due to clinical PD and diagnostic imaging can not be performed, the day of clinical PD will be defined as the day of progression.
- Surviving patients, who are not assessed as progression will be censored on the last day when no progression is confirmed on imaging (last day of PFS confirmed) (If information on progression or progression-free is obtained from medical institutions to which the patients are transferred or referred, a statement on medical information provision documenting the rationales for a diagnosis should be received and retained. Notification only by telephone will not be acceptable.).
- For patients who died without being assessed as progression, whether to consider to be an “event on the day of death” or “censoring on the last day of PFS confirmed” should be decided at the time of data review performed prior to data fixation. In principle, they should be “an “event on the day of death” unless the period from the last day of PFS confirmed to the day of death is long.
- When another treatment is given as subsequent treatment in withdrawals due to AEs or refusal, they should be censored on the start day of the subsequent treatment.
- The development of secondary cancer (asynchronous double cancer) should not be handled as an event or censoring but as PFS until other events are observed.

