5.2. Precautions for registration

- 1) Registration after start of the protocol treatment is not allowed without exception.
- 2) When confirmation of the contents of registration/eligibility confirmation sheet is inadequate, registration is not accepted until all the requirements are satisfied.
- 3) After confirmation of eligibility, a registration number is issued. Registration is completed upon issuance of the registration number.

- 4) When registered once, subject's registration is not cancelled (deletion from the database) except for cases of retraction of consent inclusive of rejection of the use of data for research. The initial registration information (registration number) is adopted in any cases of overlapped registration.
- 5) When erroneous registration/overlapped registration have been proved, this should be promptly informed.
- 6) When subjects are visiting other hospitals or departments continuously at the time of registration, inform the relevant investigator to the effect that the said subjects participate in this clinical trial.

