6.1. Protocol Treatment

In the present trial, the protocol treatment will consist of the investigational drug, Lenvatinib, used in combination with Pembrolizumab. However, in the event that the termination criteria are satisfied for one of these drugs, the trial investigator can consider continuing the treatment protocol with either Lenvatinib or Pembrolizumab monotherapy upon deliberation with the trial coordinating committee. Each patients will undergo study treatment on an inpatient or outpatient basis.

The treatment protocol will commence within 14 days of enrollment, including the day of enrollment. Furthermore, in the event that administration of the investigational drug cannot be initiated within 14 days of enrollment (including the day of enrollment), the trial coordinating committee is to be contacted to examine how the patient should be handled.

The following terms are used in this protocol:

- Discontinuation: Investigational drug administration is not resumed.
- Treatment interruption: The protocol treatment is moved on to the next dosing schedule without administration of one or more doses of the investigational drug.
- Washout period: A period during which no investigational drug is given

6.1. 1 Study Treatment

- 1) Lenvatinib will be administered with water orally once a day (with or without food) in 21-day cycles at approximately the same time each day. On Day 1 of each cycle, in case concomitantly administered, it will be administered approximately within 1 hour after completion of pembrolizumab administration. Pembrolizumab will be administered as a dose of 200 mg as a 30-minute IV infusion, Q3W (25 minutes to 40 minutes are acceptable).
- 2) The initial dose of Lenvatinib will be 20 mg per day.
- 3) Continue administration until it will fall into "6.2.1. Discontinuation Criteria for the Protocol Treatment".

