11.2.4. Overall survival: OS

The period will be from the day of enrollment, as the starting date of the computation, to the day of death of any cause.

Surviving patients should be censored on the last day of PFS confirmed (Confirmation of survival by telephone inquiry will be acceptable. However, the fact of confirming survival should be documented in medical records.).

Patients who are lost to follow up should be censored on the last day when their survival is confirmed before being lost to follow up.

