12.2. Definitions of Analysis Populations

Each analysis population is defined as follows:

Abbreviation	Analysis population	Definition
All Enrolled Patients (ITT)	Intention to treat	Analysis target group based on the principle of Intention to treat. A population of enrolled patients excluding those with overlapping or incorrect enrollment
SP	Safety Population	A population of all enrolled patients who received at least one dose of the protocol treatment
FAS	Full Analysis Set	A population of all enrolled patients who met the entry criteria and received protocol treatment

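### PFS and OS in the FAS start at enrolment although FAS entry requires a later first dose, which adds a small amount of immortal time; the ITT curves are unaffected

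*Combined protocol and SAP*

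**What the plan says.** Time origin. Section 11.2.2 (PFS): "The period will be from the day of enrollment, as the starting date of the computation, to the day when progression is determined". Section 11.2.4 (OS): "The period will be from the day of enrollment, as the starting date of the computation, to the day of death of any cause".

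Analysis sets, section 12.2. The FAS is: "A population of all enrolled patients who met the entry criteria and received protocol treatment". The ITT set carries no dosing condition: "A population of enrolled patients excluding those with overlapping or incorrect enrollment".

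Gap between enrolment and first dose. Section 5.2 fixes the order: "Registration after start of the protocol treatment is not allowed without exception". Section 6.1 sets the window: "The treatment protocol will commence within 14 days of enrollment, including the day of enrollment". For a later start, "the trial coordinating committee is to be contacted to examine how the patient should be handled".

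Use of the sets. The synopsis plans PFS and OS in both the ITT set and the FAS, and section 12.11.1 has the study report present efficacy for all enrolled patients and for the FAS. Section 12.5.2 specifies ordinary Kaplan-Meier estimation. Nowhere do the documents give a first-dose origin, delayed entry or a landmark for the FAS curves, and they do not say which set carries the main PFS/OS result.

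**The concern.** Membership of the FAS is settled by something that happens after the clock has started. A patient who dies between enrolment and first dose is never in the FAS, while every FAS patient has that interval credited as time alive. The enrolment clock suits the ITT set, but it does not suit a set selected on later treatment unless the selection is allowed for.

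What is at stake is the reading of two secondary endpoints. The trial has one arm, and section 12.4 calls the treatment promising if ORR exceeds 10% and the secondary endpoints also show improvement. The FAS is the set for the primary analysis, so its PFS and OS curves could easily become the ones quoted. A removable offset that always points upward is undesirable there, even a small one.

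**Working it through.** **1. The plan's own figure.** The documents give no expected value, precision or power for PFS or OS. The only design figure is the two-stage ORR design in section 2.10.2: 10 + 19 = 29 FAS patients, continue with at least 2 responses in 10, succeed with at least 6 in 29, p0 = 0.10, p1 = 0.30, one-sided 5%, power 80%. With X ~ Bin(10, p) and Y ~ Bin(19, p), P(success) is the sum over x = 2 to 10 of P(X = x) × P(Y ≥ max(0, 6 − x)).

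- At p = 0.10: 0.0471. At p = 0.30: 0.8051.
- Probability of stopping early under p0: 0.736. Expected N: 10 + 19 × (1 − 0.736) = 15.0.
- A search over designs returns the same optimal design.

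The design reproduces. No time origin enters it, so nothing below changes it.

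**2. Length of the gap.** Fourteen days counting the enrolment day means a first dose 0 to 13 days later. 13 / 30.44 = 0.43 month. This is the planned maximum, not a hard cap, because later starts go to the coordinating committee.

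**3. What can happen in the gap, for a FAS patient.**

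- Death: impossible, since the patient was later dosed.
- Progression on a scheduled scan: none is scheduled, because section 8.6 counts post-baseline scans from the start of treatment, the first at week 6.
- Clinical progression: section 11.2.2 counts it only when treatment is discontinued for it and imaging is not possible, so it needs treatment to have begun.
- Progression on an unscheduled scan before dosing: not excluded by sections 11.2.2 or 12.2.

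The interval is therefore strictly event-free for OS and nearly so for PFS.

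**4. Size of the shift.** Assume a constant hazard λ = ln 2 / m, where m is the median without the selection, and a delay d before dosing. Conditioning on no event before d gives

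- FAS median from enrolment = m + d
- FAS rate at t months = exp(−λ(t − d)), against exp(−λt)

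The medians m are illustrative assumptions, taken from studies of other regimens cited in sections 2.3 and 2.7. At d = 13 days for every patient:

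| Endpoint | Assumed m (months) | FAS median from enrolment | Relative shift |
|---|---|---|---|
| PFS | 2.6 | 3.03 | +16.4% |
| PFS | 5.6 | 6.03 | +7.6% |
| PFS | 6.6 | 7.03 | +6.5% |
| OS | 11.4 | 11.83 | +3.7% |

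The absolute shift is 0.43 month in every row. Six-month rates at d = 13 days:

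- PFS with m = 5.6: 50.2% instead of 47.6%.
- OS with m = 11.4: 71.3% instead of 69.4%.

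If delays are uniform over 0 to 13 days (assumed), the shift is about 6.5 days, 6.5 / 30.44 = 0.21 month. The medians become 5.81 (PFS, m = 5.6) and 11.61 (OS, m = 11.4).

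**5. Scale.**

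- Expected deaths before dosing among 29 patients, all waiting 13 days, with median OS 11.4: 29 × (1 − exp(−ln 2 × 0.427 / 11.4)) = 29 × 0.0256 = 0.74.
- Approximate 95% interval for an exponential median with 29 events, m × exp(±1.96/√29): 3.9 to 8.1 months around 5.6, and 7.9 to 16.4 around 11.4.

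The shift is small beside this sampling error.

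**The case against.** The strongest reply is that the plan already contains the remedy. The ITT curves run from enrolment, carry no dosing condition and will be reported beside the FAS curves. Enrolment is a defined and consistent origin, and the plan nowhere claims to estimate time on treatment. With one arm, no comparison group loses person-time to the other. The shift lies well inside the sampling error, and the 13-day figure needs every patient to wait the full window. A footnote to Table 8.2 lets tests done before enrolment, within 7 days of dosing, serve as day 1 tests, so shorter gaps are contemplated. Giving the FAS its own clock also has a price: ITT and FAS would differ in origin as well as in population, and patients lost before dosing would still be excluded.

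Most of this stands and sets the weight of the point. It does not remove it. The documents do not name ITT as the main PFS/OS analysis, and the FAS curves as specified contain the offset, which is a bias and not noise.

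A reader might go further and infer that the FAS curves cannot be compared with published curves that start at first dose. The documents do not support that. They give no time origin for any study they cite, and they specify no formal PFS or OS comparison or threshold.

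**Conclusion.** The point holds as a minor one. As written, the FAS analysis of OS contains immortal time before first dose, and the FAS analysis of PFS very nearly does. The shift is upward and at most 0.43 month within the planned window under constant hazard. It is about 0.2 month if delays are uniform, and could be larger for a patient whose late start the committee accepts. The percentages depend on assumed medians, because the documents state none for this trial.

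Two stronger readings should be resisted. One is that every FAS patient is guaranteed free of progression until dosing; the guarantee is strict only for death. The other is that the trial's conclusion on its primary endpoint is affected; ORR, its error rates and the sample size do not involve this clock.

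**What to change.** State in sections 11.2.2 and 11.2.4 and in the SAP that the ITT analysis from enrolment is the main analysis of PFS and OS, and that the FAS curves are supportive. For the FAS curves, specify one of two methods:

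- Delayed entry (left truncation): keep the enrolment clock and let each patient join the risk set on the day of first dose. PFS and OS keep one origin across both sets. With about 29 patients the earliest risk sets will be small, and the method cannot inform the days before the first patient is dosed. If all patients waited equally long it would change nothing.
- First dose of either study drug as time zero. This is simpler and removes the interval entirely, but ITT and FAS results then differ in clock as well as in population, and the report should say so.

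Neither method restores patients lost before dosing; the ITT analysis covers them.

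The cost is a sentence in each place. First-dose dates are already collected (Table 8.1), and no visit, scan or patient is added. FAS medians will come out slightly shorter.
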